**Table 16. Outcome and Event Dates for Time to LRF Analysis**

Scenario	Date of event/censoring	Outcome
No adequate baseline assessment and no LRF and no death	Date of randomization	Censored
No adequate post-baseline tumor assessment or clinical evaluation and no death	Date of randomization	Censored
LRF or death	Date of LRF or death	Event
No LRF and no death	Date of last adequate tumor assessment or clinical evaluation documenting no LRF	Censored

The time to LRF in Arm A and Arm B will be compared based on the FAS using the strata assigned at randomization and using a 1-sided stratified log-rank test at 1-sided nominal alpha level of 0.025.

The treatment effect will be estimated using a Cox's Proportional Hazard model stratified by the randomization strata to calculate the hazard ratio. Each stratum will define a separate baseline hazard function (using the 'STRATA' statement in SAS PROC PHREG), ie, for the i-th stratum the hazard function is expressed as:  $h(i;t) = h(i,0;t) \exp(x\beta)$ , where  $h(i,0;t)$  defines the baseline hazard function for the i-th stratum and  $x$  defines the treatment arm (0=Arm B, 1= Arm A) and  $\beta$  is the unknown regression parameter.

Ties will be handled by replacing the proportional hazards model by the discrete logistic model (Ties=Discrete option in SAS PROC PHREG).

Kaplan-Meier estimates (product-limit estimates) will be presented by treatment arm together with a summary of associated statistics including the median LRF time with 2-sided 95% CIs. In particular, the LRF rates at 12, 24, 36, 48 and 60 months will be estimated with corresponding 2-sided 95% CIs. The CIs for the median will be calculated according to

Brookmeyer and Crowley (1982) and the CIs for the survival function estimates at the time points defined above will be derived using the log-log transformation according to Kalbfleisch and Prentice (2002) (conftype=loglog default option in SAS Proc LIFETEST) with back transformation to a CI on the untransformed scale. The estimate of the standard error will be computed using Greenwood’s formula.

Frequency (number and percentage) of patients with each event type (LRF or death) and censoring reasons will be presented by treatment arm.

Reasons for censoring will be summarized according to the categories in Table 17 following the hierarchy shown.

**Table 17. Time to LRF Censoring Reasons and Hierarchy**

Hierarchy	Condition	Censoring Reason
1	No adequate baseline assessment AND no LRF AND no death	No adequate baseline assessment
2	No event and [withdrawal of consent date ≥ date of randomization OR End of study (EOS) = Patient refused further follow-up]	Withdrawal of consent
3	No event and lost to follow-up in any disposition page	Lost to follow-up
4	No event and [EOS present OR disposition page for any epoch after screening says patient will not continue into any subsequent phase of the study] and no adequate post-baseline assessment	No adequate post-baseline assessment
5	No event (no LRF AND no Death) AND Distant Metastatic (DM) failure	Distant Metastatic failure only
6	No event and none of the conditions in the prior hierarchy are met	Ongoing without an event

#### 6.2.2.5. Distant metastatic failure

Distant metastatic failure or distant metastasis (DM) is defined as new tumor identified at a site distant from the head and neck anatomic region or draining lymph nodes.

Time to DM is defined as the time from the date of randomization to the date of the first documentation of metastatic disease progression per RECIST v1.1 or death due to any cause, whichever occurs first. DM data will be censored on the date of the last adequate tumor assessment or clinical evaluation for patients who do not have an event (DM or death); the analysis will consider any DM or death as an event regardless of the number of prior missing tumor assessments or clinical evaluations or timing of the event with respect to initiation of anti-cancer therapy.

The censoring and DM event date options to be considered are presented in Table 18.

$$DM \text{ (months)} = [\text{date of event or censoring} - \text{date of randomization} + 1] / 30.4375$$

**Table 18. Outcome and Event Dates for Time to DM analysis**

Scenario	Date of event/censoring	Outcome
No adequate baseline assessment and no DM and no death	Date of randomization	Censored
No adequate post-baseline tumor assessment or clinical evaluation and no death	Date of randomization	Censored
DM or death	Date of DM or death	Event
No DM and no death	Date of last adequate tumor assessment or clinical evaluation documenting no DM	Censored

The time to DM in Arm A and Arm B will be compared based on the FAS using the strata assigned at randomization and using a 1-sided stratified log-rank test at 1-sided nominal alpha level of 0.025.

The treatment effect will be estimated using a Cox's Proportional Hazard model stratified by the randomization strata to calculate the hazard ratio. Each stratum will define a separate baseline hazard function (using the 'STRATA' statement in SAS PROC PHREG), ie, for the i-th stratum the hazard function is expressed as:  $h(i;t) = h(i,0;t) \exp(x\beta)$ , where  $h(i,0;t)$  defines the baseline hazard function for the i-th stratum and  $x$  defines the treatment arm (0=Arm B, 1= Arm A) and  $\beta$  is the unknown regression parameter.

Ties will be handled by replacing the proportional hazards model by the discrete logistic model (Ties=Discrete option in SAS PROC PHREG).

Kaplan-Meier estimates (product-limit estimates) will be presented by treatment arm together with a summary of associated statistics including the median DM time with 2-sided 95% CIs. In particular, the DM rates at 12, 24, 36, 48 and 60 months will be estimated with corresponding 2-sided 95% CIs. The CIs for the median will be calculated according to Brookmeyer and Crowley (1982) and the CIs for the survival function estimates at the time points defined above will be derived using the log-log transformation according to Kalbfleisch and Prentice (2002) (conftype=loglog default option in SAS Proc LIFETEST) with back transformation to a CI on the untransformed scale. The estimate of the standard error will be computed using Greenwood's formula.

Frequency (number and percentage) of patients with each event type (DM or death) and censoring reasons will be presented by treatment arm.

Reasons for censoring will be summarized according to the categories in Table 19 following the hierarchy shown.

**Table 19. Time to DM Censoring Reasons and Hierarchy**

Hierarchy	Condition	Censoring Reason
1	No adequate baseline assessment AND no DM AND no death	No adequate baseline assessment
2	No event and [withdrawal of consent date $\geq$ date of randomization OR End of study (EOS) = Patient refused further follow-up]	Withdrawal of consent
3	No event and lost to follow-up in any disposition page	Lost to follow-up
4	No event and [EOS present OR disposition page for any epoch after screening says patient will not continue into any subsequent phase of the study] and no adequate post-baseline assessment	No adequate post-baseline assessment
5	No event (no DM AND no Death) AND Locoregional (LRF) failure	Locoregional failure only
6	No event and none of the conditions in the prior hierarchy are met	Ongoing without an event

#### 6.2.2.6. Neck dissection

A patient who had neck dissection can be identified by the “Surgery Details –Salvage Surgery Neck” eCRF. If the box “Yes” was checked for the question “Was neck dissection performed as expected per protocol?”, the patient had a neck dissection.

The rate of neck dissection on each treatment arm will be estimated by dividing the number of patients with neck dissection recorded from randomization until PD per modified RECIST v1.1 or death due to any cause by the number of patients randomized to the respective treatment arm. The corresponding exact 2-sided 95% CIs will be provided by treatment arm.

The rate of pathologically-positive neck dissection and rate of pathologically-negative neck dissection will be summarized using the same methodology as for the rate of neck dissection.

The final pathology of neck dissection (positive or negative) can be identified from the “Outcome” field in the “Pathology Details” eCRF with “Lesion number” and “Date of sample” matching “Lesion number” and “Date of neck dissection” in the “Surgery Details – Salvage Surgery Neck” eCRF.

- Positive pathology includes the following outcomes from the “Pathology Details” eCRF: (1) live tumor cells present, or (2) 10% or greater vital tumor tissues.
- Negative pathology includes the remaining outcomes: (3) no live tumor cells present, (4) complete tumor regression, no evidence of vital tumor tissues, (5) less than 10% vital tumor tissue, or (6) not consistent with disease under study.

The outcome of the pre-surgery biopsy sample (positive or negative) can be identified from the “Outcome of biopsy” field in the “Biopsy Sample Details” eCRF with “Lesion number” and “Date of biopsy sample” matching “Lesion number” and “Date of pre-surgery biopsy sample” in the “Surgery Details –Salvage Surgery Neck” eCRF.

The positive and negative predictive values (PPV and NPV respectively) of the biopsy to the final pathology will be calculated based on the subset of patients who had neck dissection and a pre-surgery biopsy sample (matching lesion number and date).

- $PPV = TP / (TP + FP)$  where TP is the number of lesions with true positive pre-surgery biopsy (pre-surgery biopsy positive and positive pathology) and FP is the number of lesions with false positive pre-surgery biopsy (pre-surgery biopsy positive and negative pathology).
- $NPV = TN / (TN + FN)$  where TN is the number of lesions with true negative pre-surgery biopsy (pre-surgery biopsy negative and negative pathology) and FN is the number of lesions with false negative pre-surgery biopsy (pre-surgery biopsy negative and positive pathology).

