### **9.3.2.7. Neck Dissection**

The rate of neck dissection on each treatment arm will be estimated by dividing the number of patients with neck dissection recorded from randomization until PD per modified RECIST v1.1 or death due to any cause by the number of patients randomized to the respective treatment arm. The corresponding exact 2-sided 95% CIs will be provided by treatment arm.

The rate of pathologically-positive neck dissection and rate of pathologically-negative neck dissection will be analyzed in the same way as the rate of neck dissection.

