### 5.2.6. Definition of start of new anti-cancer therapy

The start date of new anti-cancer therapy is the earliest date after randomization amongst the following:

- Start date of anti-cancer drug therapy recorded in the ‘Follow-up Cancer Therapy’ eCRF pages
- Start date of radiation therapy recorded in ‘Follow-up Radiation Therapy’ eCRF pages with ‘Treatment Intent’ = ‘Curative in intent’
- Surgery date recorded in ‘Concomitant Surgery’, and ‘Follow-up Surgery’ eCRF pages when ‘Surgery Outcome’ = ‘Resected’ or ‘Partially Resected’.

When start date of anti-cancer therapy is missing or partially missing, the imputation rules described in Section 5.3.3.4 should be applied using ‘Follow-up Cancer Therapy’, ‘Follow-up Radiation Therapy’, ‘Concomitant Surgery’, and ‘Follow-up Surgery’ eCRF pages.

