#### **6.2.2.7. Pathologic complete response**

Pathologic complete response (pCR) is defined as the absence of histologically identifiable residual cancer in any resected specimen and will be summarized separately for randomized patients who underwent salvage surgery at the primary site and for randomized patients who had neck dissection. Further, a cross tabulation of pCR at the primary site (responder, not a responder, no salvage surgery) and in the neck (responder, not a responder, no salvage surgery) will be provided.

Patients who underwent salvage surgery are identified in the “Surgery Details – Salvage Surgery Primary Site” or “Surgery Details – Salvage Surgery Neck” with answer “Yes” to “Was salvage surgery at primary site performed?” or “Was neck dissection performed as expected per protocol?”, respectively.

Pathologic complete responders are patients who underwent, prior to PD per modified RECIST v1.1, salvage surgery/ neck dissection with a negative pathology, ie, with outcome in “Pathology Details eCRF” as “no live tumor cells present”, “complete tumor regression”, “no evidence of vital tumor tissues”, “less than 10% vital tumor tissue”, or “not consistent with disease under study”. Patients should be matched based on the lesion number and date of the sample if the “Pathology Details eCRF” and date of the surgery at the primary site/date of neck dissection.

If more than one lesion was resected prior to PD per modified RECIST v1.1, a pathologic complete responder is a patient with 1) no resected lesion with a positive pathology AND 2) with at least one resected lesion with negative pathology.

The pCR rate at primary site/neck in each treatment arm will be estimated by dividing the number of patients with pCR recorded at any visit from randomization until PD per modified RECIST v1.1 or death due to any cause by the number of randomized patients who had salvage surgery at the primary site/neck dissection, respectively, in each treatment arm. The corresponding exact 2-sided 95% CIs will be provided by treatment arm.

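### The SAP identifies neck dissections through an eCRF item that mixes occurrence with protocol conformity, so dissections performed otherwise may be missed

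*SAP*

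**What the plan says.** Protocol 9.3.2.7 estimates the rate in each arm by "dividing the number of patients with neck dissection recorded from randomization until PD per modified RECIST" v1.1, or death, by the number randomized to that arm. It attaches no condition on how the dissection was done.

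SAP 6.2.2.6 repeats that formula, dividing "by the number of patients randomized to the respective treatment arm", but adds an identification rule. It begins "A patient who had neck dissection can be identified by the" Salvage Surgery Neck page of the eCRF, and then takes a 'Yes' to "Was neck dissection performed as expected per protocol" to mean that the patient had a dissection. The SAP gives no other rule and does not define 'No' or a missing answer.

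SAP 6.2.2.7 uses the same 'Yes' to identify neck surgery for pathologic complete response (pCR). For the primary site it uses a plain occurrence item, "Was salvage surgery at primary site performed". The pCR rate for each site is then divided "by the number of randomized patients who had salvage surgery at the primary site/neck dissection, respectively, in each treatment arm". The positive and negative predictive values (PPV, NPV) of pre-surgery biopsy in 6.2.2.6 are limited to patients with a neck dissection and a matched biopsy.

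**The concern.** The protocol endpoint asks whether a dissection was done. The SAP's item can be read as asking whether it was done in the way the protocol expects. Read that way, a patient who was operated on, but differently, is not picked up by the only rule given.

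Protocol 3.4 sets several expectations that a real operation might not meet: a consolidation dissection is confined to the areas initially involved, the surgical investigator is to be contacted beforehand, and a primary treatment dissection falls within 140 days of completing CRT. One flag feeds three sets of results: the dissection rate with its pathology-positive and pathology-negative components, neck pCR, and biopsy PPV/NPV. Neck dissection and pCR are named secondary antitumor endpoints.

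**Working it through.** The documents state no expected dissection rate, pCR rate or predictive value, so there is no planned figure to reproduce. The check compares the texts, followed by an illustration on assumed inputs.

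**Texts side by side**

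1. Numerator. Protocol 9.3.2.7: any recorded dissection before PD or death. SAP 6.2.2.6: the same formula, with patients found through 'Yes' to the combined item. The SAP does not announce a narrower endpoint.
2. Neck against primary site. In SAP 6.2.2.7 the primary-site item asks only about performance; the conformity wording is on the neck item alone.
3. Where a 'No' goes. The neck side of the pCR cross-tabulation has three categories: responder, non-responder and no salvage surgery. A patient operated on but answered 'No' fits only the last.
4. Which cases could be affected. Candidates are a consolidation dissection wider than the areas initially involved, one not discussed beforehand with the surgical investigator, and a late dissection with negative pathology. The last matters because, under Protocol 3.3, a dissection after 140 days is PD only if tumor is present. A late negative one, with no earlier PD, therefore stays inside the counting window and would be a neck pCR.

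**Effect on the dissection rate (illustration)**

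Inputs: about 640 patients randomized 1:1 (Protocol 3.1; SAP 2.2), so 640 / 2 = 320 per arm. The true counts and *f*, the share of performed dissections answered 'No', are assumptions.

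Reported rate = true count × (1 − *f*), rounded to whole patients, / 320.

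| True count (rate) | *f* = 10% | *f* = 30% |
|---|---|---|
| 16 (5.0%) | 14/320 = 4.4% | 11/320 = 3.4% |
| 32 (10.0%) | 29/320 = 9.1% | 22/320 = 6.9% |
| 64 (20.0%) | 58/320 = 18.1% | 45/320 = 14.1% |

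For the middle row the exact 95% CI goes from 6.9–13.8% (32 patients) to 6.2–12.8% (29) or 4.4–10.2% (22). At *f* = 0 nothing changes. The error can go only downwards.

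**Effect on neck pCR (illustration)**

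With the SAP's denominator, a missed patient leaves numerator and denominator together. Assume 32 dissections, 19 of them pathology-negative, and 6 answered 'No'. The full rate is 19/32 = 59.4%. After the loss it depends on how many of the 6 were negative:

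- none: 19/26 = 73.1%
- four: 15/26 = 57.7%
- all six: 13/26 = 50.0%

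PPV and NPV behave in the same way: they lose lesions, and they change only if the lost lesions differ from those kept.

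**The case against.** The strongest reply is that the SAP gives a sufficient condition ('Yes' means a dissection took place) and nowhere says that 'No' is scored as no dissection. The eCRF, its response options and its completion guidance are not in the documents. Protocol 3.4 itself expects a dissection in certain patients, so the item may simply ask whether the expected operation was performed. On that reading nothing is lost. This stands, and it is why the size may be zero. It does not remove the point: SAP 6.2.2.7 identifies operated patients by that 'Yes' alone, and a programmer following the text has no other category for a 'No'.

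Two further limits also stand. The protocol leaves the extent of surgery for recurrence, progression or primary-site salvage to the treating surgeon, so a wide dissection there is not a departure. And 140 days separates a primary treatment dissection from a salvage one; it is not in itself a conformity rule. A late dissection with tumor present is already a PD event, so it adds little to a rate counted only until PD. The affected types are therefore narrower than every wide or late operation.

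A reader might infer that the missed cases differ between arms, so that equal true rates would look unequal. The documents give no mechanism for this: the trial is double-blind, and for these endpoints only per-arm rates with exact confidence intervals are planned, with no test between arms.

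**Conclusion.** The stated rule, read plainly, is narrower than the protocol's endpoint and leaves 'No' undefined. Dissections performed otherwise than expected may be missed. If so, the neck-dissection rate is understated, while neck pCR and PPV/NPV rest on a selected subset with no predictable direction of error.

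The size cannot be derived from the documents. The figures above rest on assumed dissection rates and an assumed share answered 'No'.

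Two stronger conclusions are tempting and are not supported. One is that non-conforming dissections are counted as not done, so that the results are wrong; that depends on how sites used an item whose form is not available. The other is that the omissions are related to outcome; that is possible but not shown. Nor is any effect on PFS, OS or time to locoregional failure shown: late salvage dissection with tumor enters PFS as a PD subtype collected in the eCRF (SAP 6.1.1.1), and nothing ties that subtype to this item. The point is confined to secondary, descriptive results, but it merits a correction because the text departs from the protocol and the remedy is small.

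**What to change.** In SAP 6.2.2.6 and 6.2.2.7:

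- Define a neck dissection as any record with a date of neck dissection on the Salvage Surgery Neck page, whatever the answer to the conformity item. SAP 6.2.2.6 already uses that date to match pathology.
- State what 'No' and a missing answer mean.
- Cross-check against the Concomitant Surgery and Follow-up Surgery pages where these identify a neck procedure. SAP 5.2.6 shows only a date and an outcome being used from those "eCRF pages when ‘Surgery Outcome’ = ‘Resected’ or ‘Partially Resected", so whether they can identify a neck dissection needs confirming.
- Report the conformity answer and the timing (up to 140 days, or later, after CRT) only as a descriptive breakdown.

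The cost is SAP wording and programming. One thing to confirm is that the form records the date when the answer is 'No'; if it does not, the cross-check carries the definition. If every operated patient was answered 'Yes', the change alters no result.

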#### **6.2.2.7. Pathologic complete response**

Pathologic complete response (pCR) is defined as the absence of histologically identifiable residual cancer in any resected specimen and will be summarized separately for randomized patients who underwent salvage surgery at the primary site and for randomized patients who had neck dissection. Further, a cross tabulation of pCR at the primary site (responder, not a responder, no salvage surgery) and in the neck (responder, not a responder, no salvage surgery) will be provided.

Patients who underwent salvage surgery are identified in the “Surgery Details – Salvage Surgery Primary Site” or “Surgery Details – Salvage Surgery Neck” with answer “Yes” to “Was salvage surgery at primary site performed?” or “Was neck dissection performed as expected per protocol?”, respectively.

Pathologic complete responders are patients who underwent, prior to PD per modified RECIST v1.1, salvage surgery/ neck dissection with a negative pathology, ie, with outcome in “Pathology Details eCRF” as “no live tumor cells present”, “complete tumor regression”, “no evidence of vital tumor tissues”, “less than 10% vital tumor tissue”, or “not consistent with disease under study”. Patients should be matched based on the lesion number and date of the sample if the “Pathology Details eCRF” and date of the surgery at the primary site/date of neck dissection.

If more than one lesion was resected prior to PD per modified RECIST v1.1, a pathologic complete responder is a patient with 1) no resected lesion with a positive pathology AND 2) with at least one resected lesion with negative pathology.

The pCR rate at primary site/neck in each treatment arm will be estimated by dividing the number of patients with pCR recorded at any visit from randomization until PD per modified RECIST v1.1 or death due to any cause by the number of randomized patients who had salvage surgery at the primary site/neck dissection, respectively, in each treatment arm. The corresponding exact 2-sided 95% CIs will be provided by treatment arm.

### 6.2.2.8. Objective response

**Best overall response (BOR)** will be assessed based on reported overall lesion responses at different evaluation time points from the date of randomization until the first documentation of PD, according to the following rules.

